2.4.5.3 Multiplicity issues

Not applicable.

2.4.6 Analyses of safety data

The all-treated population will be used for all safety analyses except for the DLT analysis in Phase 1, which will be performed based on the DLT-evaluable population.

2.4.6.1 Analyses of DLTs (Phase 1 only)

The DLTs will be listed by patient using the DLT-evaluable population in Phase 1.

2.4.6.2 Analyses of adverse events

The primary focus of adverse event reporting will be on treatment-emergent adverse events. Pre-treatment and post-treatment adverse events will be described separately.

If an AE date of onset (occurrence, worsening, or becoming serious) is incomplete, an imputation algorithm will be used to classify the AE as pretreatment, treatment-emergent, or post-treatment. The algorithm for imputing date of onset will be conservative and will classify an AE as treatment emergent unless there is definitive information to determine it is pretreatment or post-treatment. Details on classification of adverse events with missing or partial onset dates are provided in [Section 2.5.3](#).

Regarding treatment discontinuation, following definitions will be used:

- **Premature** treatment discontinuation is defined when 1 of the IMPs is permanently discontinued, subjects will continue receiving the other IMP until study treatment permanent discontinuation
- **Definitive** treatment discontinuation is defined as the discontinuation of all the study drugs

The severity grade will be taken into account in the summary. For patients with multiple occurrences of the same AE, the maximum (worst) severity grade by period of observation will be used. Summaries will be provided for all grades and for Grade ≥ 3 (including grade 5). Missing grades handling is provided in [Section 2.5.3](#).

Sorting within tables should ensure the same presentation for the set of all AEs for each observation period (pre-treatment, treatment-emergent and post-treatment). For that purpose, tables of all TEAEs by SOC and PT will be sorted by the internationally agreed SOC order and decreasing frequency of PTs within SOCs. This order will define the presentation order for all other tables unless otherwise specified.

Overall summary of TEAEs

An overall summary of TEAEs will be provided. The number (%) of patients who experience any of the following will be provided:

- TEAE
- TEAE of Grade ≥ 3
- TEAE of Grade 5
- Serious TEAE
- Treatment-related TEAEs (any grade)
- Treatment-related TEAEs of \geq Grade 3
- Serious treatment-related TEAEs
- TEAE leading to definitive study treatment discontinuation
- TEAE leading to premature discontinuation of isatuximab
- TEAE leading to premature discontinuation of REGN2810
- AESI
- AESI of Grade ≥ 3

Analysis of all TEAEs

The number (%) of patients experiencing TEAEs by primary SOC and PT will be summarized by grade (all grades and Grade ≥ 3). Similar tables will be presented for treatment-related TEAEs, serious TEAEs, and TEAEs leading to definitive/premature discontinuation.

TEAEs with an incidence $\geq 5\%$ will be summarized by PT for all grades and Grade ≥ 3 .

Listings of serious TEAEs, TEAEs leading to definitive or premature treatment discontinuation will be provided.

Infusion associated reactions (IARs)

IAR analysis will include all adverse events regardless of relationship to isatuximab, cemiplimab or NIMP. The IARs will be summarized as follow:

- Number (%) of patients experiencing IARs according to investigator reported AEs presented by primary SOC and PT will be summarized by grade,
- Description of the IAR diagnoses (using the diagnosis reported and excluding symptoms)
 - Number (%) of patients action taken
 - Number (%) of patients with only 1, ≥ 1 , ≥ 2 , ≥ 3 , ≥ 4 and ≥ 5 episodes
 - Number (%) of patients with first occurrence of IAR at the first infusion and subsequent infusions
 - Number (%) of patients with IAR at the first and subsequent infusions
 - Number (%) of patients with at least two episodes of IARs at the same infusion
 - Day of onset from infusion
 - Duration (in days)
- Number of patients with symptoms of IARs (as reported by investigator) by SOC and PT

Analysis of adverse events of special interest

A listing of patients with at least one AESI described in [Section 2.1.4.2](#) will be provided.

Analysis of pre-treatment and post-treatment adverse events

The following analysis will be provided by grade (all grades and Grade ≥ 3).

- All pre-treatment AEs by primary SOC and PT, showing the number (%) of patients with at least 1 pre-treatment AE, sorted by the internationally agreed SOC order and decreasing incidence of PTs within each SOC
- All post-treatment AEs by primary SOC and PT, showing the number (%) of patients with at least 1 post-treatment AE, sorted by the internationally agreed SOC order and decreasing incidence of PTs within each SOC

2.4.6.3 Deaths

The following summaries of deaths will be generated:

- Number (%) of patients who died by study period (on-treatment, post-treatment) and reasons for death (disease progression, AE, other)
- TEAEs with fatal outcome (on the AE eCRF page as reported by the Investigator), and TEAEs with fatal outcome during the post-treatment period summarized by SOC and PT

2.4.6.4 Analyses of laboratory variables

Each laboratory test result will be graded by CTCAE criteria (version 4.03), when applicable. For hematological parameters and for some biochemistry parameters, Sanofi sponsor generic normal ranges will be used for the grading of laboratory abnormalities (see list of parameters in [Table 6](#) and [Table 7](#)). For other biochemistry parameters (eg, for hepatic parameters), grading will be derived using the local laboratory normal ranges.

The number (%) of patients with abnormal laboratory tests at baseline and during the on-treatment period will be presented by all grades and each grade. For patients with multiple occurrences of the same laboratory variable during the on-treatment period, the maximum grade (worst) per patient will be used.

The denominator used for percentage calculation is the number of patients with at least 1 evaluation of the laboratory test during the considered observation period.

When appropriate, the summary table will present the frequency of patients with any grade of abnormal laboratory tests and with Grade 3-4 abnormal laboratory tests.

2.4.6.5 Analyses of vital sign variables

The incidence of vital signs potentially clinically significant abnormality (PCSA) ([Table 4](#)) any time during the on-treatment period will be summarized by treatment group irrespective of the baseline level and/or according to the following baseline status categories:

- Normal/missing
- Abnormal according to PCSA criterion or criteria

Table 4 - Potentially clinically significant abnormalities criteria for vital signs

Parameter	PCSA
HR	≤50 bpm and decrease from baseline ≥20 bpm ≥120 bpm and increase from baseline ≥20 bpm
SBP	≤95 mmHg and decrease from baseline ≥20 mmHg ≥160 mmHg and increase from baseline ≥20 mmHg
DBP	≤45 mmHg and decrease from baseline ≥10 mmHg ≥110 mmHg and increase from baseline ≥10 mmHg
Weight	≥5% increase from baseline ≥5% decrease from baseline

Temperature and respiratory rate will be summarized at baseline and end of treatment. A listing of patients with at least one PCSA will be provided.

2.4.6.6 Analyses of electrocardiogram variables

A listing of patients with ECG results will be provided.

2.4.6.7 Analysis of Immunogenicity

Immunogenicity analysis will be done separately for isatuximab and REGN2810.

Number of evaluable patients, number (%) of pre-existing ADA and negative patients at baseline, number (%) of boosted and induced patients (either transient, persistent or indeterminate) will be reported, along with descriptive statistics of titer, by cohort and possibly overall. Prevalence and incidence will also be presented.

In addition, for positive ADA patients, time to onset, duration of ADA response, and the characterization of the immune response (transient, persistent, indeterminate) will be provided.

An individual data listing with ADA samples status (positive, negative or inconclusive), the titer if applicable, date of first/last dose, duration of exposure, study period, cycle/day, time point and date/time of sampling along with C_{trough} value of the drug will be provided for all patients.

The impact on safety and efficacy endpoints may be further explored by graphical methods or descriptively, depending on the ADA prevalence.

2.4.7 Analyses of pharmacokinetic variables

PK analysis will be done separately for isatuximab and REGN2810.

2.4.7.1 PK parameters

2.4.7.1.1 Cycle 1

Following the first administration, individual concentrations and PK parameters of drug will be listed and summarized by descriptive statistics (such as the number of observations, arithmetic and geometric mean, median, SD, SEM, CV%, minimum, and maximum) by cohort and possibly overall.

Individual and mean concentration profiles over time will be plotted by cohort and possibly overall under the responsibility of Sanofi, Pharmacokinetic, Dynamic and Metabolism (PKDM), Translational Medicine and Early Development (TMED) department.

2.4.7.1.2 Overall treatment: C_{trough} and C_{eoI}

C_{trough} defined as a sample collected before dosing, and in a time window of 12 to 16 days after the previous infusion for the Q2W administration, or in a time window of 6 to 8 days after the previous infusion for the QW administration will be included in the descriptive analysis irrespectively of interruption of infusion. However C_{trough} drawn outside collection of time window described in the protocol PKPD flowchart or collected after dose deviation higher than $\pm 50\%$ from intended dose will be excluded from the analyses.

C_{eo} collected after significant infusion interruption, drawn outside collection of time window described in the protocol PKPD flowchart or collected after dose deviation higher than $\pm 50\%$ from intended dose will be excluded from the analyses.

Individual C_{trough} and C_{eo} will be listed and summarized with same descriptive statistics as above by cohort and possibly overall.

Mean ($\pm SE$) of C_{trough} will be plotted over treatment phase by cohort and possibly overall for isatuximab and for REGN2810.

Individual C_{trough} ratio and C_{eo} ratio (described in [Table 5](#)) will be listed and summarized by descriptive statistics by cohort and possibly overall as described above.

Table 5 - C_{trough} and C_{eo} ratio

Analyte	C_{trough}	C_{eo}
Isatuximab	C2D1 vs C1D8	C2D1 vs C1D1
	C4D1 vs C1D8	C4D1 vs C1D1
REGN2810	C4D1 vs C1D22	C4D1 vs C1D1

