Tumor genetic markers (blood) W		Х			X (Cycle 2 and Cycle 3 only)	Х			
Immunophenotyping (blood) X		Х			X (Cycle 2, Cycle 3, then every other cycle)	Х	Х		
Plasma or serum cytokines (blood) y	Х	Х			X (Cycle 2, Cycle 3, then every other cycle)	Х	Х		
Disease Assessment									
- CT/MRI Z	Х				X (repeat every 9 weeks)	Х		Х	
- PSA assessment aa	Х	x k			X (repeat every 9 weeks)	Х		Х	
- Bone scan bb	Х				X (repeat every 9 weeks)	Х		Х	
Isatuximab Administration CC		Х	Χ	Χ	X				
REGN2810 Administration CC		Х			X				
AE/SAE Assessment dd	Х	Continuously throughout study period		iod			, new related AE/SAEs)		
Prior/Concomitant Medication	X (within 28 days prior to first dose)		Continuously throughout study period X (related to AE/SAEs)			AE/SAEs)			
New anticancer therapy						Х	>	1	Х
Survival status								Х	X

- a **Evaluation:** Assessments to be performed prior to study treatment and prior to premedication administration unless otherwise indicated. Inform consent should be signed before any study specific procedures. It can be signed more than 28 days prior to enrollment/randomization. Screening time indicates the time frame in which study procedures used to support eligibility have to be done prior to enrollment/randomization.
- b **Cycle:** A cycle is 21 days. The treatment window is ±1 day for each of the weekly administrations and ±2 day for each of the Q3W administrations. A dose is deemed to have been delayed if the treatment is ≥2 days beyond the theoretical day of treatment for Q3W dose. The window for blood chemistry, hematology, urinalysis, PSA assessment (Cycle 1 Day 1 only), and biomarker blood draw is within 1 day prior to IMP administration (where applicable) for Cycle 1 and beyond.
- c Follow-up: Patients who discontinue the study treatment without PD will be followed every 90 days for disease assessment until confirmation of PD or start of treatment with another anti-cancer therapy, or until study cut-off date, whichever comes first. The further follow-up schedule beyond 90 days after last dose of IMP is according to the disease progression status:
  - Patients who discontinue study treatment due to PD: phone call follow-up will be done every 90 days from the date of last IMP administration until death or study cut-off date.

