#### 4.3.2 Schedule and dose of administration

REGN2810 is administered as an intravenous (IV) infusion every 3 weeks at 350 mg dose.

A flat IV REGN2810 dose of 350 mg once every 3 weeks (Q3W) was selected, based on population pharmacokinetics (PK) modeling and simulation, as it is expected to provide exposure that closely replicates that observed in patients (mean weight: 80 kg) for the 3 mg/kg Q2W IV regimen in the ongoing first-in-human study R2810-ONC-1423 (NCT02383212). Simulations of REGN2810 exposure in 1000 patients using population PK analyses indicated that:

- A 350 mg Q3W dose in patients resulted in similar (≤20% difference) Ctrough, AUC12 weeks, and Cmax as compared to the 3 mg/kg Q2W dose in the first-in-human patient population (80 kg), and exceeded those observed at the 1 mg/kg Q2W dose.
- The variability in REGN2810 exposure (coefficient of variation) was similar for body-weight adjusted doses as compared to flat doses.

Given the similar predicted exposure for 350 mg Q3W when compared to the 3 mg/kg Q2W regimen, a similar efficacy/safety profile is also expected. Therefore, the 350 mg Q3W IV dose of REGN2810 is being proposed across the REGN2810 program.

In patients with MM, isatuximab exhibits non-linear PK due to the presence of target mediated drug disposition. In addition, tumor burden impacts the PK of isatuximab.

Based on safety, efficacy, PK, and PK/pharmacodynamic analyses, the dose/schedule of isatuximab when used in combination with other therapies for the treatment of MM is 10 mg/kg QW × 4 followed by Q2W. The half-life of isatuximab associated to the linear elimination is 18 days and we hypothesized that the immuno-modulatory mechanisms of isatuximab will be mainly involved in the pharmacological activity of isatuximab; therefore, a less intensive schedule of administration for isatuximab is proposed compared to the schedule used in patients with MMs: 10 mg/kg QW × 3 followed by Q3W. Of note, based on updated pharmacokinetic characterization of isatuximab in 2019, the plasma half-life has been re-estimated to 28 days.

Based on internal safety, efficacy, PK, and PK/pharmacodynamic data analyses, the dose/schedule of isatuximab when used as monotherapy for the treatment of MM is 20 mg/kg QW × 4 followed by Q2W. However, based on the reasons mentioned above and the hypothesis that tumor burden will be lower in patients with prostate cancer compared to MM (ie, less target-mediated drug

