#### 5.2 SECONDARY OBJECTIVES

- To evaluate the safety of the combination of isatuximab with REGN2810 or isatuximab monotherapy.
- To evaluate the immunogenicity of isatuximab and REGN2810.
- To characterize the PK profile of isatuximab single agent or in combination with REGN2810, and to characterize the PK of REGN2810 in combination with isatuximab.
- To assess overall efficacy of isatuximab in combination with REGN2810 or single agent (tumor burden change, duration of response [DOR], disease control rate [DCR], and progression-free survival [PFS]).

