### 6.6.2 Dose delay and dose omission

Within a cycle, the treatment window is  $\pm 1$  day for each of the weekly administrations and  $\pm 2$  days for each of the Q3W administrations. Within a cycle, a dose is deemed to have been delayed if the treatment is  $\geq 2$  days beyond the theoretical day of treatment for weekly dose, and  $\geq 3$  days beyond the theoretical day of treatment for Q3W dose. The patient will receive the next infusion after recovery of the toxicity as described in Section 6.6.3.

Patients may have dose delay, cycle delay, or dose omission if toxicity occurs and he/she does not recover according to following rules:

- In Cycle 1 (for weekly administration of isatuximab) if toxicity occurs and the patient does not recover on the day of planned infusion or within the following 3 days, infusion of isatuximab (in D8 or D15) may be omitted.
- In Cycle 2 and beyond, if toxicity occurs and the patient does not recover on the day of planned infusion or within the following 14 days, either infusion of isatuximab or REGN2810 may be omitted for combination cohort.
- In case of cycle delay or dose omissions for the recovery of toxicity, the following rules should be followed for restart or discontinue the treatment:
  - In case of a cycle delay up to 14 days or a dose omission, it is per Investigator's decision to restart the study treatment.
  - After a cycle delay of >14 days and ≤84 days, or 2 to 4 consecutive dose omissions, it is per Investigator's decision to restart the study treatment or the IMP that is omitted, if a clear benefit from therapy is observed and after consultation with the Sponsor.
  - The study treatment must be definitely permanently discontinued if the cycle delay is longer than 84 days, or if more than 4 consecutive dose omissions, the IMP will be prematurely discontinued.

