1.1.1.1 Starting dose and de-escalation design

The starting dose is selected based on past and ongoing clinical trials. Starting dose is 350 mg Q3W for REGN2810 with isatuximab given 10 mg/kg QW for 3 weeks followed by Q3W. Dose de-escalation will be performed if necessary as defined in [Table 1](#) below:

Table 1 - Dose modification for Phase 1

Dose level	Isatuximab	REGN2810
Starting dose	10 mg/kg QW x 3->Q3W	350 mg Q3W
Minus 1 (DL-1)	5 mg/kg QW x 3->Q3W	350 mg Q3W

Abbreviations: DL=dose level; QW=once weekly; Q3W=once every 3 weeks.

At the starting dose, dose limiting toxicity (DLT) will be assessed in the first 6 patients (1 cycle; 21 days):

- If $\leq 1/6$ patient has DLT, the starting dose will be the RP2D
- If $2/6$ patients have DLT, 6 additional patients will be enrolled at starting dose level:
 - If a total of $2/12$ patients treated at starting dose have DLT, starting dose will be the RP2D
 - If a total of $\geq 3/12$ patients have DLT, dose will be de-escalated to dose level minus 1 (DL-1)
- If $\geq 3/6$ patients have DLT, dose will be de-escalated to DL-1

An additional 6 patients may be enrolled at DL-1; if $\leq 1/6$ patient has DLT, DL-1 will be the RP2D. At DL-1, if $\geq 2/6$ patients have DLT, an alternative dose/schedule might be considered from a safety viewpoint by the Sponsor after consulting with the Investigators who recruit patients for the Phase 1 part.

The DLT observation period is 1 cycle (21 days). The duration of the DLT observation period will be longer for patients who delay initiation of Cycle 2 due to treatment-related adverse event (AE) for which the duration must be assessed in order to determine if the event is a DLT. All AEs during treatment, unless due to disease progression or an obviously unrelated cause, will be taken into consideration by the Sponsor and recruiting Investigators for the determination of the maximum tolerated dose (MTD) and RP2D.

Investigational medicinal product (IMP) initiation of patients in the Phase 1 part is to be staggered by ≥ 3 days. The National Cancer Institute (NCI) common terminology criteria for adverse events (CTCAE) version 4.03 will be used to assess the severity of AEs. Causal relationship is to be determined by the Investigator. The DLTs will be confirmed by the Sponsor and recruiting Investigators.

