2.1.5 Pharmacokinetic variables

The PK sampling times for isatuximab and REGN2810 were provided in the PK/PD flowchart in Section 1.5 of the protocol.

The following PK parameters (listed in [Table 3](#)) will be calculated with PKDMS software (Pharsight) V3.0, using non-compartmental method from isatuximab and REGN2810 concentrations after the first administration on Cycle 1. The parameters will include, but may not be limited to the following:

Table 3 - List of pharmacokinetic parameters and definitions

Parameters	Analyte		Definition
	REGN2810	Isatuximab	
C _{eo1}	X	X	Concentration observed at the end of intravenous (IV) infusion
C _{max}	X	X	Maximum concentration observed
t _{max}	X	X	Time to reach C _{max}
C _{last}	X	X	Last concentration observed above the lower limit of quantification
t _{last}	X	X	Time of C _{last}
AUC _{0-21d}	X		Area under the concentration versus time curve calculated using the trapezoidal method over the dosing interval (21 days)
AUC _{0-7d} or AUC _{0-21d}		X	Area under the plasma concentration versus time curve calculated using the trapezoidal method over the dosing interval (7 days, and for cohorts C and D: 21 days)

C_{trough} are defined as sample collected just before treatment administration during repeated dosing.

In addition, populations PK approaches may be used for both compounds and PK estimates may be used to conduct exploratory exposure-response analyses for safety and efficacy and PK/PD analyses for relevant biomarkers. If done, the data generated will be reported in stand-alone report(s).

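### The SAP's C_trough inclusion rule has windows for two-weekly and weekly dosing but none for three-weekly dosing, the schedule behind every REGN2810 trough and most isatuximab troughs

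*SAP*

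**What the plan says.** SAP 2.4.7.1.2 states which pre-dose samples enter the descriptive trough analysis: those taken "in a time window of 12 to 16 days after the previous infusion for the Q2W administration", or 6 to 8 days after the previous infusion when dosing is weekly. It then drops samples drawn outside the protocol flowchart's sampling window, or taken after a dose more than 50% away from the intended dose. No other interval is given there or elsewhere in the SAP.

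The same section says mean C_trough "will be plotted over treatment phase by cohort and possibly overall for isatuximab and for REGN2810". Its Table 5 lists three trough ratios: isatuximab C2D1 vs C1D8, isatuximab C4D1 vs C1D8, and REGN2810 C4D1 vs C1D22.

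SAP 2.1.5 has a broader definition with no interval: trough values "are defined as sample collected just before treatment administration during repeated dosing".

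The trial's schedule is in SAP 1.1.1.1: "Starting dose is 350 mg Q3W for REGN2810 with isatuximab given 10 mg/kg QW for 3 weeks followed by Q3W". Cohort A-2 uses the same isatuximab schedule alone. Cohorts C and D, if opened, omit the weekly start (SAP 1.1.2). In Protocol 4.3.2, two-weekly isatuximab belongs to multiple myeloma, where the combination schedule "for the treatment of MM is 10 mg/kg QW × 4 followed by Q2W".

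**The concern.** The rule has a window for a schedule nobody in this trial receives and none for the schedule that produces most of the troughs. An on-time trough about 21 days after the last infusion satisfies neither stated window, yet the section orders plots and ratios built from exactly those samples. The SAP's exposure sections (2.4.4.1 to 2.4.4.3) handle weekly and three-weekly dosing correctly, so the trough rule also conflicts with the rest of the SAP.

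What is at stake is a stated secondary objective: "To characterize the PK profile of isatuximab single agent or in combination with REGN2810, and to characterize the PK of REGN2810 in combination with isatuximab". The trough summaries, the trough-over-time plots, most of Table 5 and any exploration of ADA impact on PK (SAP 2.4.7.2) depend on which samples are kept. If the SAP does not decide, the programmer will, possibly after the concentrations have been seen.

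**Working it through.** **Inputs**

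- Stated trough windows: 6–8 days (weekly) and 12–16 days (two-weekly), SAP 2.4.7.1.2.
- Dosing days (Protocol 1.2, SAP 1.1.1.1 and 1.1.2), with 21-day cycles so that C2D1 is day 22 and C3D1 is day 43. Weekly-start isatuximab is given on days 1, 8, 15 and 22, then every 21 days. REGN2810, and isatuximab in Cohorts C and D, are given on day 1 and then every 21 days.
- Dosing tolerance, Protocol 1.3 footnote b: "The treatment window is ±1 day for each of the weekly administrations and ±2 day for each of the Q3W administrations".
- Pre-dose sampling window, Protocol 1.5 flowcharts: from 24 h before the coming infusion up to its start.

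**Step 1. Reproduce the stated windows.** 7 ± 1 = 6–8 days and 14 ± 2 = 12–16 days. Both match the SAP.

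**Step 2. Interval since the previous infusion, on schedule**

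| Pre-dose sample | Interval (days) | Window met |
|---|---|---|
| Isatuximab, weekly start: C1D8, C1D15, C2D1 | 8−1 = 7; 15−8 = 7; 22−15 = 7 | 6–8 |
| Isatuximab, weekly start: C3D1 onward | 43−22 = 21, then 21 each | none |
| REGN2810: C2D1 onward | 22−1 = 21, then 21 each | none |
| Isatuximab, Cohorts C/D: C2D1 onward | 22−1 = 21, then 21 each | none |

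**Step 3. Count per fully sampled patient**

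| | Qualifying, to C6D1 | Qualifying, over 35 cycles (730/21 = 34.8) |
|---|---|---|
| REGN2810 | 0 of 5 | 0 of 34 |
| Isatuximab, weekly start | 3 of 7 | 3 of 36 |
| Isatuximab, Cohorts C/D | 0 of 5 | 0 of 34 |

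Under the SAP 2.1.5 definition, every one of these samples is kept.

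**Step 4. Table 5.** Isatuximab C2D1 vs C1D8 is fully covered, since both samples are at 7 days. Isatuximab C4D1 vs C1D8 has a 21-day numerator with no window. REGN2810 C4D1 vs C1D22 has no window for either term. So 2 of 3 ratios are affected in the combination cohorts. In monotherapy Cohort A-2, where no REGN2810 is sampled, it is 1 of 2.

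**Step 5. Does the dosing tolerance close the gap?** If ±2 days is measured from a fixed calendar, two compliant infusions can be 21−4 = 17 to 21+4 = 25 days apart. Sampling up to 24 h early extends this to 16–25 days. If tolerance is counted from the previous actual dose, the range is 19–23 days, or 18–23 with early sampling. Only the most extreme case, 16 days, touches the upper edge of the two-weekly window, so the gap remains.

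**Step 6. Why late troughs need a rule.** Protocol 6.6.2 leaves restart to the Investigator "In case of a cycle delay up to 14 days or a dose omission", and permits delays of up to 84 days after consultation with the Sponsor. A pre-dose sample could therefore be 21+84 = 105 days after the last infusion and still meet the flowchart window, because that window is set from the coming dose. As an illustration, assume mono-exponential decline at the isatuximab half-lives in Protocol 4.3.2 (18 days, re-estimated as 28). A trough taken 14 days late would then be lower by 1 − 2^(−14/18) = 42% or 1 − 2^(−14/28) = 29%.

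**The case against.** The strongest reply is that the windows are conditional on schedule. A three-weekly trough is neither two-weekly nor weekly, so the text can be read as silent rather than as excluding it. The general definition in SAP 2.1.5 and the flowchart rule would then apply. A section that orders a REGN2810 trough plot cannot intend to delete every REGN2810 trough. This is fair: 0 of 5 is the literal extreme, not the likely outcome. But on that reading three-weekly troughs have no limit on interval at all, while weekly ones are held to ±1 day, so the rule is still incomplete where it is most used.

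The flowchart does supply something. It places the first three-weekly trough at a nominal 504 h (21 days) after the first dose for REGN2810, and for isatuximab in Cohorts C and D. That covers only Cycle 2 Day 1; from Cycle 3 there is no nominal interval. The permitted sampling window at 504 h is still tied to the coming infusion.

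Three qualifications stand:

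- The 17–25 day range depends on how the ±2 days is anchored. For the first interval the first dose is the anchor, so ±2 applies once.
- The counts do not apply to patients without PK sampling: NSCLC patients enrolled in Phase 2 Stage 1 after Amendment #5, and the cross-over part. The sponsor may also reduce or stop isatuximab sampling.
- Concentrations are collected regardless, and population PK may be used, so no data are lost.

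These limit the consequence; they do not remove the error.

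**Conclusion.** The rule is wrong as written. It specifies a two-weekly window that fits no cohort and omits the three-weekly window that all REGN2810 troughs, isatuximab troughs from C3D1 in the weekly-start cohorts, and all Cohort C and D isatuximab troughs require. Depending on which SAP section is followed, usable on-schedule troughs to C6D1 range from 0 to 5 of 5 for REGN2810 and from 3 to 7 of 7 for weekly-start isatuximab. These counts assume on-schedule dosing and full sampling.

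The consequence is limited to secondary, descriptive PK. No hypothesis test, stage decision, recommended Phase 2 dose, response rate or safety output depends on it, and the Cycle 1 PK parameters and C_eoi ratios are unaffected. It should be corrected before the trough outputs are programmed.

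**What to change.** In SAP 2.4.7.1.2, replace the two-weekly window with a three-weekly one and keep 6–8 days for troughs that follow a weekly dose. State that the three-weekly window covers all REGN2810 troughs, isatuximab troughs from C3D1 in the weekly-start cohorts, and all Cohort C and D isatuximab troughs. Make SAP 2.1.5 refer to this rule so that one definition governs.

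The sponsor should choose and justify the width. Following the SAP's own pattern, 21 ± 2 = 19–23 days is one example, but it would drop some compliant samples if tolerances accumulate (16–25 days in Step 5), so the anchoring should be stated too. Add a sentence on troughs after a delayed cycle or an omitted dose: excluded, or listed and summarized separately.

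The cost is one or two lines of SAP text and one program filter. Only the analysis window changes; dosing and sampling do not.
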